### ANTICIPATED TIME FRAME

Estimated patient accrual time is 1 year with data collection to occur over 30 days from randomization of each patient. Data analysis and manuscript production will occur within 6 months of the completion of data collection.

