propose a registry-based randomized clinical trial through the Americas Hernia Society Quality Collaborative (AHSQC). The AHSQC is a multicenter, nationwide quality improvement effort with the mission of improving the quality of hernia care [16]. We hypothesize that a TAP block with Exparel®, performed intraoperatively by a surgeon during open ventral hernia repair with mesh placed in retromuscular position, will result in decreased opioid requirements, reduced immediate and extended postoperative pain scores, shorten length of hospital stay, and improved quality of life when compared to a TAP block with Bupivacaine hydrochloride or placebo (normal saline), performed in the same manner and in the same population.

The aims of this study are:

Specific Aim #1: To determine if intra-hospital opioid requirements over initial 72 hours differ following the administration of Exparel®, Bupivacaine hydrochloride, or placebo (normal saline) through a TAP block during open ventral hernia repair with retromuscular mesh placement.

Opioid consumption will be assessed by measuring the cumulative dose of opioids administered through intravenous and oral preparations. Intravenous opioids will include all opioids infused through a patient-controlled analgesia device (PCA) and intravenously as a rescue medication for breakthrough pain. Specific time points for assessments are: at post-anesthesia care unit (PACU/POD0), and daily during the hospital stay up to a maximum of 7 days. Opioid requirements will be recorded and converted into morphine equivalents for standardization. In addition, we aim to record and analyze: (1) amount of opioids administered intraoperatively by the anesthesiologist, (2) cumulative dose of opioids during the first 7 days of hospital stay and (3) time to first oral opioid use.

Specific Aim #2: To determine if immediate and extended pain scores differ following the administration of Exparel®, Bupivacaine hydrochloride, or placebo (normal saline) through a

TAP block during open ventral hernia repair with retromuscular mesh placement. Immediate time points include while patients are at PACU/POD0, and daily during the hospital stay up to a maximum of 7 days. An extended time point includes 30-days postoperatively.

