AHSQC patient-reported outcomes, at baseline and postoperative day 30 ( $\pm$  15 days). The PROMIS pain intensity questionnaire is a National Institutes of Health-developed validated tool that focuses on patient-reported outcomes of pain characteristics. This survey will be completed by patients in person during enrollment, and either in person, by telephone interview or virtual visit for 30-day follow-up, if a patient is unable to come to the clinic during the defined time frame (30days $\pm$ 15days).

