### **Secondary Outcomes of Interest**

Secondary outcomes of interest include the length of hospital stay and Patient-Reported Quality of Life (PRQOL). Both information is already routinely collected through the AHSQC. Length of hospital stay will be recorded in days. PRQOL will be assessed using the HerQLes survey. [20] The HerQLes is a 12-item, validated, a hernia-specific survey that assesses quality of life through abdominal wall function after ventral hernia repair. HeQLes scores will be assessed at baseline and 30 days after the operation. This tool is also part of the patients reported outcomes of the AHSQC.

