**Randomization**

Patients will be randomized using a computer-generated random allocation sequence, by the investigational pharmacy personnel. The random allocation sequence will be implemented with REDCap®, where a randomization allocation table will be generated and uploaded into REDCap® by the study statistician listed in this protocol. Randomization will occur during the operation at the end of adhesiolysis, and at the beginning of abdominal wall reconstruction, to allow for sufficient time for the investigational pharmacy to prepare and dispense the assigned intervention. This study will be double-blinded since patients will be blinded to their assigned intervention until their participation in the study is complete, and also surgeons will be blinded to the intervention assigned to the subject. Only the investigational pharmacy will be aware of the

assigned intervention and this information will be stored in the appropriate randomization platform in REDCap. The study coordinator and other research personnel who will be abstracting opioids doses and pain scores from patients will also be blinded to the intervention that was assigned to patients.

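### The per-patient collection period is given as 30 days, but the 30-day pain score may be taken up to day 45, HerQLes has no window, and the 30-day comparisons make no use of the baseline scores

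*Combined protocol and SAP*

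**What the plan says.** Five parts of the combined protocol and SAP bear on the timing and analysis of the 30-day scores.

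- **Anticipated Time Frame.** One year of accrual is estimated, with "data collection to occur over 30 days from randomization of each patient".
- **Primary outcomes of Interest.** The PROMIS Pain Intensity 3a survey is taken at baseline and at postoperative day 30, with a tolerance of 15 days either side. A telephone or virtual contact may replace the visit "if a patient is unable to come to the clinic during the defined time frame".
- **Secondary Outcomes of Interest.** For quality of life, "HeQLes scores will be assessed at baseline and 30 days after the operation". No tolerance is stated, although this section and the one above place both questionnaires among the registry's patient-reported outcomes.
- **Randomization.** "Randomization will occur during the operation at the end of adhesiolysis". The same section says that "patients will be blinded to their assigned intervention until their participation in the study is complete".
- **Statistical Analysis.** Pain scores and quality of life are compared by Mann-Whitney U test. No role is given to the baseline score or to the day on which the follow-up score was taken.

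The specific aims in the Introduction give the later pain assessment as a nominal day: "An extended time point includes 30-days postoperatively".

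**The concern.** The only per-patient duration in the plan is shorter than the window allowed for one of its own assessments. Someone applying the 30-day period as a rule would stop collecting while the PROMIS score could still validly be obtained. Someone applying the PROMIS window would go on to day 45. For HerQLes, staff cannot tell whether a day-40 form counts when a day-40 PROMIS form does. The decision on which late forms count should be made before data are seen.

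The end of participation, which governs when a patient may learn the assigned arm, is not defined either. Both 30-day instruments are self-reported, so that point should be fixed explicitly.

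The analysis also leaves information unused. Both questionnaires are taken at baseline, but the named test compares the groups without them. Whatever correlation exists between baseline and 30-day scores is given up as precision.

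At stake are the extended pain time point of Aim 2 and the quality-of-life comparison of Aim 4.

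**Working it through.** **1. Do the two clocks start together?** The collection period runs from randomization and the PROMIS window from the operation. Randomization is intraoperative, so day 30 on one is day 30 on the other. No offset closes the gap.

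**2. The window.** Inputs: centre 30 days and tolerance 15 days (Primary outcomes of Interest); collection period 30 days (Anticipated Time Frame).

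- Earliest permitted day: 30 − 15 = 15
- Latest permitted day: 30 + 15 = 45
- Days in the window, both ends counted: 45 − 15 + 1 = 31
- Days up to and including day 30: 30 − 15 + 1 = 16
- Days after day 30: 45 − 30 = 15
- Share after the stated collection period: 15/31 = 48.4% (15/30 = 50% in continuous time)
- Latest relative to earliest: 45/15 = 3 times as long after surgery

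To cover the window, collection would have to run to day 45, 15 days longer than stated.

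**3. How much could the spread of assessment days matter?** The documents do not say how fast scores change between days 15 and 45, so this step rests on assumptions: assessment days spread evenly over the window, the same timing in every arm, and a linear change of *s* standard deviations over the 30 days. A uniform spread over a range *s* has variance *s*²/12, so total variance relative to no timing spread is 1 + *s*²/12. The power column starts from a comparison of two means that would have 80% power at two-sided alpha 0.05. That is a reference value only, because the trial was not powered on these scores.

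| *s* (SD per 30 days, assumed) | Relative variance | Power, from 80% |
|---|---|---|
| 0.25 | 1 + 0.0625/12 = 1.005 | 79.8% |
| 0.5 | 1 + 0.25/12 = 1.021 | 79.2% |
| 1.0 | 1 + 1/12 = 1.083 | 76.8% |

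If visits cluster near day 30, the loss is smaller.

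**4. Baseline adjustment.** For a linear model with baseline as covariate, the residual variance is about (1 − ρ²) times that of the unadjusted score, where ρ is the correlation between baseline and 30-day score. The documents give no value for ρ, so the gain cannot be sized here. In large samples there is no loss at ρ = 0 and a gain at any other value.

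**5. Reach.** The primary outcomes cover the first 72 hours, and the Power Calculation rests on opioid consumption during the hospital stay. Neither uses a 30-day score, so the stated 54 per arm and 162 in total do not change.

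**The case against.** The strongest reply is that the Anticipated Time Frame section is a planning paragraph. It sets out accrual, data collection and writing-up, and it sets no cut-off and discards no score. The outcome section is the specific rule, and it provides remote contact to help obtain the survey. On this view, 30 days is simply a label for the 30-day visit, and a missing HerQLes window is an omission, not a contradiction.

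Much of this stands, and it rules out several stronger inferences that a reader might draw:

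- *Late responders will be dropped.* Only a reading that lets the planning sentence override the outcome definition gives this result.
- *Patients will be unblinded at day 30 and then score themselves.* Blinding lasts until participation is complete, and a patient who still owes the survey has not plausibly completed it. No section ends participation or schedules disclosure at day 30.
- *Visit timing will bias the comparison between arms.* The window is tied to the operation in every arm, and patients and data abstractors are blinded. The documents give no mechanism for timing to differ by arm.
- *The wide window adds large noise.* The pace of recovery over these weeks has no source in the documents. The gap between a day-15 and a day-45 patient is also not the average noise, which is much smaller, as the table shows.

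It can also be said that adjusting the main comparison for assessment day would condition on something that happens after randomization. That is fair, and it is a reason to keep assessment day out of the main analysis. It does not apply to the baseline scores, which precede randomization.

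What the reply leaves untouched is that the two timing statements differ, that no text reconciles them, that HerQLes has no window, and that the collected baseline scores go unused.

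**Conclusion.** The point holds as a minor inconsistency. Taken literally, 15 of the 31 days allowed for the 30-day PROMIS score (48%) lie beyond the stated collection period, HerQLes has no tolerance, and the 30-day scores are compared without baseline. The count needs no assumption beyond the plan's own figures and the intraoperative randomization.

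Its reach is limited to the extended pain time point of Aim 2 and to Aim 4. The in-hospital pain scores of Aim 2, the 72-hour primary outcomes and the sample size are unaffected. The documents do not support a conclusion that the 30-day results will be biased or that blinding will be broken. Under the assumed rates of change, timing spread costs between 0.2 and 3.2 percentage points from a nominal 80% power (80 − 79.8 and 80 − 76.8). The case for change therefore rests on clarity and on the precision available from baseline, not on a large loss from the window itself.

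**What to change.** 1. **Anticipated Time Frame:** state that data collection and participation, and so patient blinding, run until the 30-day questionnaires are complete or day 45, whichever is first.
2. **Secondary Outcomes of Interest:** give HerQLes the same ± 15-day window as PROMIS.
3. **Statistical Analysis:** compare 30-day PROMIS and HerQLes scores adjusted for their own baseline value, for example by ANCOVA, or by rank-based ANCOVA if the scores are skewed.
4. **Assessment day:** record the actual postoperative day of each questionnaire, and use it only in a supportive sensitivity analysis.

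The cost is up to 15 more days of follow-up for late responders and slightly more analysis work. Baseline scores are already planned. The documents do not say whether the registry stores the date of each questionnaire, so one extra data field may be needed. No change in sample size follows.

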### PATIENT RISKS AND DISCOMFORTS

As with any surgical procedure, patients may experience pain, bleeding, and discomfort. Common occurrences following hernia repair include seroma, hematoma, inflammation, wound dehiscence, and infection. Risks of Bupivacaine Hydrochloride include allergic reactions, arrhythmias, chest pain or pressure, dizziness, confusion, restlessness, tinnitus, blurred vision, dyspnea, seizures, nausea, emesis, and lethargy. Risks of Exparel® include nausea, vomiting, constipation, as well as (rarely) seizures and cardiac arrest. Patients receiving placebo intraoperatively will not necessarily experience higher levels of pain, as all individuals,

Version #4 8/15/2019  
NCT03541941

regardless of intervention arm, will be provided a multimodal pain management regimen with patient-controlled analgesia postoperatively.

### PATIENT BENEFITS

There are no direct benefits to subjects for participation in this study. Subject participation will, however, help physicians and hospital administrators better understand the outcomes of Exparel® use concerning postoperative pain management and its influence on opioid consumption, hospital length of stay and quality of life.

### COSTS TO THE SUBJECTS

There are no extra costs to the subjects associated with this research endeavor. Procedures related to preoperative evaluation, hernia repair, and postoperative monitoring are considered standard of care and will be the responsibility of the subject and the subject's insurance company.

### ALTERNATIVES TO PARTICIPATION

Patients are under no obligation to participate in this study. A member of the research team will discuss all available surgical options with patients. It will be emphasized that refusal to participate in this study will not impact any patient's ability to receive surgical care at the Cleveland Clinic Foundation.

### PAYMENTS TO SUBJECTS

There will be no payment for the subjects for the participation in this study.

## POWER CALCULATION

Sample size and power calculation for this study were performed by an experienced statistician. Our primary outcome of interest on this study is to determine if Exparel® is able to decrease the total amount of opioids used during the entire hospital length of stay, especially in the first 72 hours where Exparel® should be acting. We have hypothesized that when compared to placebo, Exparel® will confer a 30% decrease in total opioid consumption during hospital stay. This was defined by clinical judgment since there is a lack of published data reporting a clinically significant reduction in opioid requirements as a consequence of other interventions. Additionally, other protocols studying Exparel® have also hypothesized that the intervention would confer the same degree of opioid use reduction. Considering a 30% reduction in total opioids consumption, an alpha of 0.05, a beta of 0.20, our study will need a sample size of 49 patients per arm to achieve a statistical power of 80%. To account for losses of follow-up during the study, we have included a 10% drop-out rate in our power calculations to anticipate the latter.

Considering a 10% dropout, the total sample size for this study will be 54 patients per arm. Therefore, the total is 162 subjects.

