## OUTCOMES OF INTEREST

### **Primary outcomes of Interest**

Primary outcomes of interest are opioid requirements and pain scores over initial 72 hours of the postoperative period. Opioid requirements will be assessed by measuring the cumulative dose of opioids administered intravenously (infused through a patient-controlled analgesia device as well as the quantity of opioids administered intravenously as rescue, if needed) and the quantity of opioids administered through oral preparations. This will be assessed at time points: at day of surgery (while patients are at PACU or the nursing floor), at postoperative days 1, 2 and 3. Additional time points include daily assessments during the rest of the hospital stay up to a maximum of 7 days. The total dose of opioids used at each time point will be recorded and converted into morphine equivalents for standardization and analysis. We will record the cumulative dose of opioids from 0 hours to 72 hours after the operation and for the total hospital length of stay (up to a maximum of 7 days). In addition, we aim to record the dose of opioids administered intra-operatively by the anesthesiologist, time for first oral opioid dose over the first 72 hours (discontinuation of PCA), and the percentage of patients not requiring opioids over the first 72 hours.

Pain scores will be determined using a 100mm visual analog scale (VAS). The VAS is a 100mm horizontal line with two endpoints: 0 (no pain) and 100 (worst imaginable pain). While in the hospital, subjects are to assess, “How much pain are you experiencing right now?” Pain scores will be assessed at baseline during preoperative evaluation, at day of surgery (PACU or nursing floor), at postoperative days 1, 2 and 3. Additional time points include daily assessments during the rest of the hospital stay up to a maximum of 7 days.

Additional pain scores will be obtained using the Patient-Reported Outcome Measurement Information System (PROMIS) Pain Intensity 3a survey, which is part of the

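### The power calculation names whole-stay opioid use as primary, the outcomes section names 72-hour opioid use and 72-hour pain, and nothing ranks them

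*Combined protocol and SAP*

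**What the plan says.** Three places in the combined protocol and SAP bear on the primary endpoint.

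- **Primary outcomes of Interest** declares two outcomes over one window: "Primary outcomes of interest are opioid requirements and pain scores over initial 72 hours of the postoperative period". It goes on: "We will record the cumulative dose of opioids from 0 hours to 72 hours after the operation", and the same sentence also records the whole-stay total, capped at 7 days. VAS pain is scored "at day of surgery (PACU or nursing floor), at postoperative days 1, 2 and 3".
- **Introduction, Specific Aim #1** is "To determine if intra-hospital opioid requirements over initial 72 hours differ" between the three arms. The 7-day cumulative dose is listed there as an additional measure.
- **Power Calculation** gives the primary outcome as a decrease in the "total amount of opioids used during the entire hospital length of stay, especially in the first 72 hours where Exparel® should be acting". Its hypothesis is that, against placebo, "Exparel® will confer a 30% decrease in total opioid consumption during hospital stay". The 49 per arm and 80% power follow from that hypothesis. Pain is not mentioned.

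**Statistical Analysis** assigns Mann-Whitney tests to pain scores and opioid requirements. It states no time window, no order of testing, no alpha allocation and no success rule. **Secondary Outcomes of Interest** lists only length of stay and quality of life, so whole-stay opioid use is not classed as secondary anywhere.

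**The concern.** A reader who asks which result decides the trial gets two answers: 72-hour opioid use together with 72-hour pain, or whole-stay opioid use. Two things follow.

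First, the 80% power is stated for the whole-stay total. The two opioid totals are different quantities: the Introduction reports a mean stay of 5.14 days under the recovery pathway, so the whole-stay window usually runs past 72 hours. Neither 72-hour outcome has its own effect size, variability or power.

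Second, without a hierarchy, a p-value below 0.05 on 72-hour opioids, whole-stay opioids or 72-hour pain could each be reported as the primary result. Pain adds further freedom, because it is scored on the day of surgery and on days 1 to 3 and no single summary is named.

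**Working it through.** **1. What the stated sample size implies.** Inputs from Power Calculation: alpha 0.05, power 0.80, 49 per arm, 30% reduction. Two-sided testing and equal SDs are assumed, since sidedness and SD are not given. From n = 2(z₀.₉₇₅ + z₀.₈₀)²/d²:

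- d = √(2/49) × (1.960 + 0.842) = 0.566.
- With d = 0.30/CV (SD relative to the placebo mean), the implied CV is 0.30/0.566 = 0.53.
- An exact t-test gives d = 0.572 (CV 0.52). Mann-Whitney under normality (efficiency 3/π) gives d = 0.585 (CV 0.51). A one-sided test by the formula above gives d = 0.502 (CV 0.60).

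The 49 can therefore be back-solved but not verified. The dropout step reproduces: 49 × 1.10 = 53.9, so 54 per arm and 54 × 3 = 162.

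**2. Power for 72-hour opioid use.** The documents give no CV, so it is varied here as an assumption. Mann-Whitney test, 49 per arm, two-sided 0.05, 30% reduction:

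| Assumed 72-hour CV | Normal, equal SDs | Lognormal, constant CV (simulated) |
|---|---|---|
| 0.45 | 89% | about 98% |
| 0.60 | 67% | about 86% |
| 0.70 | 54% | about 77% |

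The columns differ because the standardised effect differs. At CV 0.60 it is 0.30/0.60 = 0.50 in the normal model. In the lognormal model it is |ln 0.7|/√ln(1 + 0.60²) = 0.357/0.555 = 0.64. The documents fix neither model.

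**3. False-positive risk if either 72-hour primary suffices.** Two tests at 0.05, per arm comparison: 1 − 0.95² = 0.0975 if independent, and 0.091 at an assumed correlation of 0.5.

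**4. Power under the possible rules for two primaries**, at the effect that has 80% power at 0.05:

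- *Either suffices, alpha 0.025 each:* Φ(2.802 − 2.241) = Φ(0.56), about 71%. Restoring 80% needs 2(2.241 + 0.842)²/0.566² = 59.3, so 60 per arm before dropout. With the plan's own allowance, 60 × 1.10 = 66 per arm and 198 in total, 36 more than 162.
- *Both must succeed:* no alpha split, but joint power falls. If each had 80% power and they were independent, it would be 0.80 × 0.80 = 64%.
- *Fixed sequence, opioids first and pain second:* no alpha split and no loss of power for opioids.

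The plan does not say which rule applies.

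**The case against.** The strongest defence is that the two opioid windows are nested and the plan links them. The power section singles out the first 72 hours, and the primary outcomes section records the whole-stay total alongside the 72-hour one. This stands in part: the whole-stay total is not foreign to the primary section, and the power section itself calls it primary. The defect is therefore a disagreement over which window is primary, and it would be wrong to say that the power was computed for an unrelated endpoint. The link does not supply a 72-hour effect, mean or SD.

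A reader might infer that the trial is underpowered for 72-hour opioid use. The documents do not support that. With no CV given, power could lie on either side of 80%. Low figures such as 67% rest on normality, whereas the Statistical Analysis section expects non-normal data and uses ranks; the same CV of 0.60 gives about 86% under a skewed model.

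A reader might also infer that the type I error is already about 10%, or that 60 per arm are needed. Both hold only if success on either primary alone is enough. If both must succeed, or one is ranked first, no alpha split is required.

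**Conclusion.** The point holds as an internal contradiction with an undetermined effect on power. The primary outcomes section and Specific Aim #1 use 72 hours, the power section uses the whole stay, and the 80% is not stated for the 72-hour opioid endpoint. Pain, a declared primary, has no summary measure, target difference or power statement, and nothing ranks it against opioid use.

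The size that can be put on it is conditional: about 9.8% false positives per arm comparison for two independent primaries at 0.05 (9.1% at an assumed correlation of 0.5), if either may carry the claim. The contradiction itself rests on the text alone. The power figures are illustrations under assumed CVs, two-sided testing and an assumed distribution. The sponsor should correct this. It does not show that 162 patients are too few.

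**What to change.** Before unblinding, reconcile Primary outcomes of Interest, Power Calculation and Statistical Analysis:

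1. Name cumulative 0-72 h in-hospital morphine equivalents as the primary endpoint, and list whole-stay use (to day 7) explicitly as secondary.
2. Restate the power at 49 per arm for that endpoint, higher or lower, with the assumed mean, SD or CV, distribution, sidedness and test.
3. Name one summary of 72-hour pain, and test it second in a fixed sequence or as a key secondary outcome. Neither needs an alpha split or extra patients.
4. If pain stays an equal primary, state whether either or both must succeed and give the resulting power (about 71% at 0.025 each if either suffices).

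Cost: no new patient data, since the 0-72 h total is already recorded. The sponsor must source a 72-hour mean and SD, and the stated power may become less favourable. Under item 3 pain loses equal primary status, which is a real change from the present outcomes section.
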